## **6.2 DETERMINATION OF SAMPLE SIZE**

Approximately 70 patients need to be recruited and randomized in a 1:1 ratio to the two treatment groups (satralizumab and placebo). The sample size considerations are based on the following assumptions:

1. A two-sided log-rank test
2. 80% power at the 5% significance level
3. A 66.5% reduction in the risk of relapse, i.e., the TFR hazard ratio of satralizumab over placebo is 0.335
4. TFR in the placebo arm following an exponential distribution, with hazard rate  $h(t)=0.4184$
5. A 2-year dropout rate of 10%

Based on these assumptions, 26 TFR events are needed for the primary analysis. TFR events are defined as protocol-defined relapses confirmed by the CEC with EDSS/FSS assessment performed by the examining assessor within 7 days after relapse symptoms were reported to site by the patient. The maximum accrual rate is estimated to be approximately 8 patients per month, after the first patient in (FPI) plus 8 months of ramp up. The 70 patients enrolled over one year and followed for an additional one and a half years will provide 26 TFR events. The primary analysis will be performed once 26 TFR events have been observed. The Sponsor will conduct a blind review of the data including accumulation of events during the double-blind period and may take appropriate action such as to increase the number of patients or to extend the double-blind period based on this blind review.

It has been assumed that the number of relapses will follow a Gamma-Poisson distribution and that the variance/mean ratio will be a constant value of  $\sqrt{2}$ . This distribution was assumed and the ratio was estimated using data from MS trials (Gold et al. 2012; Kappos et al. 2010) because there are no approved medications for NMO and no raw data from patients with this indication are available.

Because the mean ARR of NMO patients is estimated at 0.753 (Cossburn et al. 2012) and patients entering this study have an ARR  $\geq 1$  owing to inclusion criterion 2, we calculate the zero-truncated mean of the Gamma-Poisson distribution with the mean of 0.75 and the mean and variance ratio of  $\sqrt{2}$ , then the baseline ARR is estimated at 1.6. The two Phase 3 MS trials above reported that pre- and post-baseline ARR in the placebo group were 1.4 and 0.4, so the post-baseline ARR in placebo group in this trial is estimated at 0.5.

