Using the proportion of zero under supposed ARR distribution, we estimate the relapse-free rate at a year in placebo group at 65.8%. The relapse-free rate is assumed to follow the exponential distribution with a constant hazard, and then we set the hazard ratio of 0.4184 in placebo group.

According to tocilizumab case reports in NMO patients, the pre- and post- baseline relapse counts were reduced from total 4 counts per 6 months to 1 count per 6 months. Then the pre- and post- baseline ratio of 0.25 is used as the estimation of the mean ARR ratio of tocilizumab compared with placebo. Moreover, the azathioprine's data showed the pre- and post- baseline mean ARR ratio was 0.33 ( $=0.77/2.32$ , the mean ARR were estimated from the median ARR and the distribution supposition above) and the rituximab data showed the pre- and post-baseline mean ARR ratio was 0.125 ( $=0.3/2.4$ ), then we estimate the rituximab mean ARR ratio compared with azathioprine at 0.38 ( $=0.125/0.33$ ).

Under the assumption of ARR and relapse-free rate distribution above, the mean ARR ratio is coincided with the hazard ratio. Tocilizumab hazard ratio data (0.25) could have a possibility of overestimation because of the case report with only three patients and the hazard ratio between rituximab and azathioprine (0.38) is the comparison with an active control, then we consider the satralizumab hazard ratio compared to placebo should exist between 0.25 and 0.38. So we have set the satralizumab hazard ratio compared with placebo at 0.335.

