According to tocilizumab case report in NMO subjects, the pre- and post- baseline relapse counts were reduced from total 4 counts per 6 months to 1 count per 6 months. Then the pre- and post- baseline ratio of 0.25 is used as the estimation of the mean ARR ratio of tocilizumab compared with placebo. Moreover, the azathioprine's data showed the pre- and post- baseline mean ARR ratio was 0.33 (= 0.77/2.32, the mean ARR were estimated from the median ARR and the distribution supposition above) and the rituximab data showed the pre- and post- baseline mean ARR ratio was 0.125 (= 0.3/2.4), then we estimate the rituximab mean ARR ratio compared with azathioprine at 0.38 (= 0.125/0.33).

Under the assumption of ARR and relapse-free rate distribution above, the mean ARR ratio is coincided with the hazard ratio. Tocilizumab hazard ratio data (0.25) could have a possibility of overestimation because of the case report with only three subjects and the hazard ratio between rituximab and azathioprine (0.38) is the comparison with an active control, then we consider the SA237 hazard ratio compared to placebo should exist between 0.25 and 0.38. So we have set the SA237 hazard ratio compared with placebo at 0.335.

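### The sample-size section labels tocilizumab's uncontrolled before-after ratio (0.25) as a ratio to placebo, so the 0.25 to 0.38 bracket used to support the design hazard ratio of 0.335 does not hold as written.

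*Protocol*

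**What the plan says.** Protocol 6.2 plans the trial on "A two-sided log-rank test", "80% power at the 5% significance level", and the assumption that "the TFR hazard ratio of satralizumab over placebo is 0.335". It needs 26 events from about 70 patients randomized 1:1.

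The control rate is built first. Baseline ARR is put at 1.6. Placebo arms in two multiple sclerosis (MS) trials fell from 1.4 to 0.4, "so the post-baseline ARR in placebo group in this trial is estimated at 0.5".

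The treatment effect comes next, from two sources:

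- **Tocilizumab.** Case reports show 4 relapses per 6 months falling to 1. "Then the pre- and post- baseline ratio of 0.25 is used as the estimation of the mean ARR ratio of tocilizumab compared with placebo".
- **Rituximab.** Its before-after ratio (0.3/2.4 = 0.125) is divided by azathioprine's (0.77/2.32 = 0.33), giving 0.38 for rituximab against azathioprine.

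Two cautions follow. The 0.25 may be an overestimate because it rests on three patients, and the 0.38 is against an active control. The Protocol then concludes that the "satralizumab hazard ratio compared to placebo should exist between 0.25 and 0.38" and sets 0.335. SAP 5.14 repeats the argument: "we consider the SA237 hazard ratio compared to placebo should exist between 0.25 and 0.38".

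**The concern.** A before-after ratio mixes the drug effect with whatever fall would have happened anyway. Patients enter because of recent relapses, so some fall after entry is expected in every arm. The section accepts this when it sets the control rate, where the placebo group is assumed to lose more than two thirds of its baseline rate. It does not remove that fall from the 0.25 before calling it a ratio to placebo. For rituximab, in the same paragraph, it does set one before-after ratio against another. The two ends of the bracket are therefore built by incompatible rules, and the lower end is mislabelled.

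What is at stake is the support for 0.335 and so for the stated 80% power. The validity of the test is not in question. The blinded review described in Protocol 6.2 looks at pooled event accumulation. It cannot show that the assumed effect is too large.

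**Working it through.** **1. Reproduce the plan.** Inputs from Protocol 6.2: two-sided 5%, 80% power, 1:1 allocation, hazard ratio (HR) 0.335.

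- Schoenfeld events = 4 × (1.960 + 0.842)² / (ln 0.335)² = 26.25, against the stated 26.
- Power with 26 events = Φ(√26/2 × |ln 0.335| − 1.96) = Φ(0.828) = 79.6%.
- Gamma-Poisson with variance/mean √2: zero-truncated mean at 0.75 is 1.61; P(0) at mean 0.5 is 65.8%; hazard −ln(0.658) = 0.4184.
- Expected events with 70 patients, uniform accrual over 1 year, 1.5 years' further follow-up and 10% dropout over 2 years: 27.0.

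All of these agree with the plan.

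**2. Before-after ratios given or implied in Protocol 6.2.**

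| Source | Ratio |
|---|---|
| Placebo group, this trial | 0.5/1.6 = 0.3125 |
| Placebo arms, MS trials | 0.4/1.4 = 0.286 |
| Tocilizumab | 0.25 |
| Azathioprine | 0.77/2.32 = 0.33 |
| Rituximab | 0.3/2.4 = 0.125 |

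**3. Apply the rituximab step throughout.**

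- Tocilizumab against placebo: 0.25/0.3125 = 0.80 (0.875 with the MS ratio 0.286).
- Tocilizumab against azathioprine: 0.25/0.33 = 0.76. This needs no MS figure.
- Rituximab against placebo: 0.125/0.3125 = 0.40 (0.44 with 0.286).
- Rituximab against azathioprine: 0.125/0.33 = 0.38, as in the plan.
- Azathioprine against placebo: 0.332/0.3125 = 1.06.

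The chosen 0.335 lies below every one of these.

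**4. What 0.335 implies.** The plan equates the mean ARR ratio with the HR. On that basis the satralizumab arm would have a before-after ratio of 0.335 × 0.3125 = 0.105. That is a larger fall than for any drug cited, rituximab's 0.125 included.

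**5. Power with 26 events**, from Φ(√26/2 × |ln HR| − 1.96):

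| HR | Power |
|---|---|
| 0.335 | 79.6% |
| 0.38 | 69.4% |
| 0.40 | 64.7% |
| 0.50 | 42.4% |
| 0.80 | 8.2% |

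**The case against.** The plan is not blind to the weakness. It says that 0.25 may overstate the effect, and it acts on that: 0.335 lies (0.335 − 0.25)/(0.38 − 0.25) = 65% of the way towards 0.38. Protocol 3.2.1 also admits that the size of the effect is not known in advance. This deserves credit, but the reason given is the number of patients. The absence of a control group is never mentioned.

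The stronger reply is that 0.38 is against an active drug, so the ratio to placebo should be lower. The plan's own figures do not bear this out. Azathioprine's 0.33 is about the same as the assumed placebo ratio of 0.3125, so rituximab against placebo comes to 0.40. The control arm here also receives baseline treatment (Protocol 3.1.1), so a comparison with an active drug is not plainly conservative.

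Against the 0.80 the objection largely stands. It carries a fall seen in MS placebo arms over to three case-report patients, and nothing in the documents shows that it applies to them. The same step makes azathioprine slightly worse than placebo (1.06), which shows how fragile the borrowed fall is. The counts are also tiny: with 1 relapse against 4, and assuming Poisson counts over equal time, an exact 95% interval for the ratio runs from roughly 0.005 to 2.5. A reader might infer that the design hazard ratio ought to have been 0.80 and that the trial had about 8% power. The documents do not support that. The 0.80 is one reworked bound, and the documents fix no single corrected value. Nor should the assumed fall from 1.6 to 0.5 be read as that of an untreated group, since the control is placebo plus baseline treatment.

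**Conclusion.** The statement that 0.25 is a ratio to placebo is wrong as written in both documents, and the 0.25 to 0.38 bracket falls with it. On the section's own figures, handled consistently, 0.335 is more optimistic than either source: about 0.38 to 0.40 from rituximab and about 0.76 to 0.80 from tocilizumab. If the true ratio were 0.38 to 0.40, power with 26 events would be about 65% to 69%, against the 80% stated.

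This rests on the plan's own assumptions: the placebo fall taken from MS trials, equality of ARR ratio and hazard ratio, and the Schoenfeld approximation. The event number, the control hazard and the power at 0.335 all reproduce, and type I error and the analysis are untouched. A reader might conclude that the sample size was miscalculated. It was not: the defect lies in how the assumed effect is justified. Protocol 1.3 records that the double-blind period is complete, so the correction is to the record and to how the stated power is read.

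**What to change.** In Protocol 6.2 and SAP 5.14:

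- Describe 0.25 as an uncontrolled before-after ratio from three patients, and remove the words that make it a comparison with placebo.
- Delete the statement that the hazard ratio should lie between 0.25 and 0.38.
- Describe 0.335 as a target effect.
- Beside the 80% figure, state power with 26 events at less favourable ratios: about 69% at 0.38, 65% at 0.40, 42% at 0.50 and 8% at 0.80.

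Do not insert 0.80 as a replacement design value. Leave the sample size and the event number as they are.

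The cost is about one paragraph in each document. The downside is that the stated justification and power become less favourable.

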### **6.3 SUMMARIES OF CONDUCT OF STUDY**

The number of patients randomized will be tabulated by study site and treatment arm. Patient disposition (the number of patients randomized, treated, and completing each study period) will be tabulated by treatment group. Study discontinuation as well as reasons for discontinuations will be summarized. Eligibility criteria deviations and other major protocol deviations will be summarized.

### **6.4 SUMMARIES OF TREATMENT GROUP COMPARABILITY**

Demographics (age, sex and race/ethnicity) and baseline characteristics (hepatitis status, baseline ARR and number of previous episodes within 2 years before enrollment) of patents will be collected at screening or baseline visit before administration of first dose of study drug.

In general, data will be summarized by treatment group and for all patients in the study (i.e., independent of treatment group). Descriptive statistics will be presented for continuous data with sample size, mean, standard deviation (SD), median, minimum, and maximum. Frequency table with percentage will be presented for discrete data.

### **6.5 EFFICACY ANALYSES**

All efficacy analyses will be based on the ITT population. Supportive evaluations will be performed using the PPS population for primary and key secondary endpoints.

#### **6.5.1 Primary Efficacy Endpoint**

The primary efficacy endpoint is TFR based on protocol-defined relapses confirmed by the CEC with EDSS/FSS assessment performed by the examining assessor within 7 days after relapse symptoms were reported to site by the patient. TFR is defined as the time from the date of the randomization until the first occurrence of relapse throughout the double-blind period. The time point of relapse onset is defined as the time at which the patient experiences any new or worsening neurological NMO representing clinical relapse(s). Events which are judged by the CEC to meet the protocol-defined relapse will be included in the primary analysis of the primary endpoint if EDSS/FSS is assessed by the examining assessor within seven days after

the patient reports the symptoms to the site. For patients who have not relapsed, not switched baseline treatment or not increased baseline treatment at the time of analysis, the TFR will be censored on the date when total number of protocol-defined relapses judged by CEC reaches 26. For patients who have switched baseline treatment or increased baseline treatment, the TFR will be censored on the date of switching or increasing the baseline treatment. For patients who have received rescue therapy without experiencing a protocol-defined relapse for which the EDSS/FSS assessment was not performed within seven days after the patient reports the symptoms to the site, the TFR will be censored on the date of receiving rescue therapy.

The primary analysis of the study is to test the equality of the TFR distribution in the satralizumab (SA237) +baseline treatment (satralizumab [SA237]) and Placebo +baseline treatment (placebo) arms:

$$H_0: TFR_{SA237} = TFR_{\text{placebo}} \text{ versus } H_1: TFR_{SA237} \neq TFR_{\text{placebo}}$$

A stratified two-sided log-rank test using strata of baseline ARR (one vs. more than one) and geographical region will be used.

The Kaplan-Meier method will be used to estimate the TFR distribution for each treatment group. The Kaplan-Meier curve will provide a visual description of the differences across treatment groups. In addition, estimates of the treatment effect will be expressed as hazard ratio and 95% confidence intervals (CIs) using a stratified (baseline ARR and geographical region) Cox proportional-hazards model. The Median TFR is not expected to be reached in this study at the time of the primary analysis; hence, every 6-months, relapse-free rates and their 95% CI will be used to describe TFR distribution in addition to the hazard ratio.

## **6.5.2 Secondary Efficacy Endpoints**

### **Key Secondary Efficacy Endpoints**

The key secondary efficacy endpoints are change in VAS for pain and change in the FACIT fatigue scale. In order to control the rate of false positive conclusions, the serial gatekeeping methodology (fixed-sequence test) will be employed to control for multiple (primary and key secondary) endpoints in this order.

#### **Change in VAS Score for Pain**

The VAS is a subjective measure of pain and it consists of a 100 mm line with two end-points representing “no pain” and “pain as bad as it could be”. Patients are asked to rate their pain by placing a mark on the line corresponding to their current level of pain. The distance along the line from the ‘no pain’ marker is then measured with a ruler giving a pain score out of 10.

The change in VAS for pain score from baseline to Week 24 in the double-blind period will be analyzed by analysis of covariance (ANCOVA) method with baseline observation carried forward (BOCF) imputation. The analysis will include the categorical effects for treatment, baseline ARR and geographical region, as well as the continuous covariates of baseline VAS for pain score.

### **Change in FACIT Fatigue Score**

FACIT fatigue scale includes 13 statements, which measures fatigue/asthenia for patients with chronic, life-threatening illnesses. For each question, a patient rates his / her condition for the past week on a 5-point Likert scale ranging from 0 (not at all) to 4 (very much). For the change in FACIT fatigue, descriptive statistics will be calculated for the change in FACIT fatigue by averaging the individual question scores.

The change in FACIT fatigue scale score from baseline to Week 24 in the double-blind period will be analyzed by ANCOVA method with BOCF imputation. The analysis will include the categorical effects for treatment, baseline ARR and geographical region, as well as the continuous covariates of baseline FACIT fatigue score.

### **Further Secondary Efficacy Endpoints**

#### **Change in Short Form Generic Health Survey (SF-36) Score**

The scores will be presented and summarized for each of the 8 domains (vitality, physical functioning, bodily pain, general health, role-physical, role-emotional, social role functioning and mental health) and 2 summary components [physical and mental]. The mean change in SF-36 domain scores will be analyzed from baseline to every 24 weeks after the baseline visit.

#### **Change in EQ-5D Score**

The EQ-5D is a participant-answered questionnaire measuring 5 dimensions of mobility, self-care, usual activities, pain/discomfort, and anxiety/depression with 3 possible response categories: 1) no problems; 2) some problems; 3) severe problems. The EQ-5D is therefore able to represent 243 (3) distinct health states. These states may then be converted into a single index value by using the time trade-off (TTO) based tariff methods. The best possible answer would be (1,1,1,1,1) and the worst possible answer would be (3,3,3,3,3). A shift table will be used to evaluate the number and percentage of patients having a different post-baseline status when compared to their baseline status. The mean change in EQ-5D score will be analyzed from baseline to every 24 weeks after the baseline visit.

#### **The Proportion of Relapse-free Patients**

The proportion of patients who are relapse-free during the double-blinded period and the entire study (*double-blind and OLE periods combined*) will be calculated for the

two treatment groups. When both periods are analyzed together, patients should be analyzed as randomized, even if patients randomized to placebo receive satralizumab in the OLE period.

The Kaplan-Meier estimates and corresponding 95% CIs for the proportion of patients who were relapse-free during the double-blind period are calculated for both treatment groups.

Relapse-free rates will be analyzed at every 24 weeks after baseline.

### **Annualized Relapse Rate**

The relapse episodes for each eligible patient will be recorded throughout the whole study. The ARR is calculated as the total number of relapses experienced divided by the person-years at risk for each year of the study period. The 95% CI will be presented based on the Poisson distribution.

For comparing the difference between *the two* treatment arms, negative binomial regression model will be used with ARR as response variable *and* treatment group, baseline ARR and geographical region as covariates.

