## **6. STATISTICAL CONSIDERATIONS AND ANALYSIS PLAN**

This section outlines the statistical analysis strategy and procedures for the study. A detailed methodology for statistical analyses of the data collected in this trial will be documented in a Statistical Analysis Plan (SAP).

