2 INTRODUCTION

This Statistical Analysis Plan (SAP) provides details of the summaries and analyses to be performed to report the results of the study. It should be read in conjunction with following documents:

- Study Protocol, Version 8.0, 17th April 2017
- Electronic Case Report Form (eCRF), Version 10.0, 30th June, 2017

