5.10.3.2 Other Secondary Endpoints

The following summary tables, figures and analysis will be provided for the ITT:

- A summary table of change in SF-36 domain scores from baseline to every 24 weeks.
- A summary table of change in SF-36 summary score (physical and mental) from baseline to every 24 weeks.
- A summary table of change in EQ-5D scores from baseline to every 24 weeks.
- A summary table of the proportion of relapse-free subjects.
- A summary table of ARR (protocol-defined relapse).

The ARR is calculated as the total number of relapses experienced divided by the person-years at risk. The 95% CI will be presented based on the Poisson distribution. ARR based on the person-years at risk on the total study period will also be provided. In order to account for different study treatment exposure durations among subjects, log-transformed exposure time will be included in the model as an “offset” variable for appropriate computation of ARR.

- A summary table of ARR (clinical relapse).
- A summary table of ARR (treated clinical relapse).
- Analysis of ARR will be performed using negative binomial regression model (protocol-defined relapse).

For comparing the difference between 2 treatment arms, relapse number will be the response variable; treatment group, baseline ARR and geographic region as covariates. Log-transformed exposure time will be included in the model as an “offset” variable.

- summary table of change in mRS scores from baseline to every 24 weeks.
- A summary table of change in ZBI scores from baseline to every 24 weeks.
- A summary table of change in EDSS scores from baseline to every 24 weeks.
- A summary table of change in visual acuity (Snellen chart) scores from baseline to every 24 weeks.

- Analysis of change in SF-36 domain scores from baseline to every 24 weeks using MMRM analysis.
- Analysis of change in SF-36 components (physical and mental) from baseline to every 24 weeks using MMRM analysis.
- Analysis of change in EQ-5D scores from baseline to every 24 weeks using MMRM analysis.
- Analysis of change in mRS scores from baseline to every 24 weeks using MMRM analysis.
- Analysis of change in ZBI scores from baseline to every 24 weeks using MMRM analysis.
- Analysis of change in EDSS scores from baseline to every 24 weeks using MMRM analysis.

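### Protocol 6.5.2 makes the annualized relapse rate itself the negative binomial response, with no exposure offset, and so conflicts with the count model in SAP 5.10.3.2

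*Protocol*

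**What the plan says.** Protocol 6.5.2 (Annualized Relapse Rate) first defines the descriptive statistic: "The ARR is calculated as the total number of relapses experienced divided by the person-years at risk for each year of the study period", with a Poisson confidence interval. To compare the arms, a "negative binomial regression model will be used with ARR as response variable"; treatment group, baseline ARR and region are the covariates. No offset or exposure weight is mentioned.

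SAP 5.10.3.2 keeps the covariates and changes the response: "relapse number will be the response variable; treatment group, baseline ARR and geographic region as covariates". It adds that "log-transformed exposure time will be included in the model as an" offset, because exposure differs between patients.

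On precedence, Protocol section 6 states: "A detailed methodology for statistical analyses of the data collected in this trial will be documented in a Statistical Analysis Plan (SAP"). The SAP introduction ties it to "Study Protocol, Version 8.0, 17th April 2017". The protocol under review is Version 11.

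The documents also differ on when double-blind time stops. Protocol 4.3.2.1 ends it at the patient's relapse or at the 26th adjudicated event. SAP 5.2 ends the efficacy period at the earliest of clinical cutoff, the day before the first extension dose, end of study, or last contact. Protocol 4.3.2.2 places that extension dose at Day 31 to 60 after onset of a treated relapse. Neither document says which clock supplies the person-years of a relapsing patient in this model.

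**The concern.** A negative binomial model describes counts, and unequal follow-up enters through an offset. If the response is a patient's own rate, every patient has the same weight whatever the follow-up, and the value for a relapsing patient depends on how soon the relapse came. In the double-blind period a patient contributes essentially 0 or 1 relapse, so the response is 0, or 1/T for a relapse at time T in years.

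Two analysts, each following one document, would report different estimates, intervals and p-values for the same listed endpoint. Which model was meant would then be settled after the data are known.

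**Working it through.** **Inputs (Protocol 6.2, repeated in SAP 5.14).** "A two-sided log-rank test"; "80% power at the 5% significance level"; hazard ratio 0.335; placebo hazard 0.4184 per year, exponential; 10% dropout at 2 years; 70 patients, 1:1, enrolled over 1 year and followed 1.5 years more; 26 events; relapses Gamma-Poisson with variance/mean √2 and placebo ARR 0.5.

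**The plan's own figures first.** No power is stated for ARR, so the check starts from the primary endpoint.
- Events (Schoenfeld): 4 × (1.96 + 0.8416)² / (ln 0.335)² = 31.40 / 1.196 = 26.25, against 26 stated. Power with 26 events is 79.6%.
- Expected events from the accrual, follow-up and dropout inputs: 27.0.
- Gamma-Poisson: shape k = 0.5 / (√2 − 1) = 1.207; P(0) = (1/√2)^k = 65.8%; −ln 0.658 = 0.4184. Both match the documents.

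**What the rate response does.** A relapse at 1 month scores 1/(1/12) = 12; one at 18 months scores 1/1.5 = 0.67. With person-time ending at relapse, the three earliest relapses carried a median of 56% of the summed rate. This fell to 38% if no relapse could occur in the first 28 days.

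**Simulation.** 3,000 trials per scenario, 35 per arm, cut at the 26th event, two-sided Wald test at 5%. Two negative binomial maximum-likelihood fits: relapse count with log-exposure offset (SAP), and relapses/person-years per patient without offset (protocol wording taken literally). One rate fit was checked against a standard package and agreed. Each cell gives SAP model / protocol wording. Coverage is at ratio 0.335.

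| Person-time rule | Type I error | Power at 0.335 | 95% CI coverage | Placebo rate per year |
|---|---|---|---|---|
| Ends at relapse, constant hazard | 3.5–4.4% / 15.6% with covariates; 4.1% / 27% without | 72–74% / 58–63% | 96% / 67–79% | 0.42 / 1.7–1.8 |
| Ends at relapse, the plan's gamma frailty | 5.0% / 14.6% | 73% / 57% | 94% / 76% | 0.37–0.41 / 1.9–2.0 |
| Runs to first extension dose | 3–4.4% / 5.0–6.5% | 71–74% / 60–63% | 96% / 90–91% | 0.36–0.41 / 0.8–0.95 |
| Boundary case: fixed follow-up, all relapses counted | 6.4% / 4.4% | 74% / 63% | 93% / 97% | 0.49 / 0.49 |

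The placebo rate is the median over trials: pooled for the SAP model, mean of patient rates for the protocol wording.

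A smaller check (400 trials per scenario, with covariates) gave power 73–74% / 59–61%. Its type I error for the protocol wording was about 15–18% with person-time ending at relapse and about 5–7% with the SAP period.

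**Why the error rate moves.** With person-time ending at relapse, no effect and covariates fitted, the rate model's log ratio had standard deviation 0.91 but a median standard error of 0.61. Very early relapses cause this. Without covariates, excluding relapses in the first 7, 14 or 28 days brings type I error from 27% to 12.9%, 9.5% or 6.9%.

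**Treatment ratio.** At a true 0.335, the rate model's median ratio was 0.26–0.36 across scenarios. The centre is roughly right; the spread is not. With person-time ending at relapse and constant hazard, the standard deviation of the log ratio was 0.96–1.17, against 0.48–0.50 for the SAP model.

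**The case against.** The strongest reply is that the matter is already handled. The protocol hands detailed method to the SAP, and the SAP specifies the count response, the offset (stated twice) and the reason for it. That stands: an analyst who follows the SAP fits the right model.

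A second reply is that the protocol never defines a per-patient ARR. Its ARR is a pooled quantity, correctly defined, so naming it as the response may be shorthand for a rate model. That is possible, but nothing in the section says so, and the literal reading is open to anyone working from the protocol alone.

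A reader might go further and infer that Version 11, being later than the SAP and having touched this sentence, replaces the SAP model. The documents do not support that. The italicised changes in the sentence are grammatical, the stated purpose of the section 6 update is the extension-period efficacy analyses, and the delegation to the SAP remains.

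A reader might also infer that the protocol wording always inflates the false-positive rate. It does not: inflation is marked only if person-time stops at relapse, is slight under the SAP period, and is absent with fixed follow-up. Nor is the treatment ratio systematically far off; it is mainly imprecise.

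**Conclusion.** The conflict is real, and the protocol's wording is the weaker of the two. Taken literally on patient-level double-blind data, it lowers power at ratio 0.335 from about 71–74% to about 57–63%. It overstates the model's placebo rate about two to four times at constant hazard (0.8–1.8 against about 0.4 per year), and somewhat more with frailty when person-time ends at relapse. Type I error is about 15–18% with covariates if person-time ends at relapse, and about 5–7% if it runs to the day before the first extension dose. The loss of power appeared in every scenario; the wrong rate appeared in every double-blind scenario but not with fixed follow-up.

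The consequence is limited. ARR lies outside the fixed sequence (time to first relapse, VAS pain, FACIT fatigue; SAP 5.10.1.4), so the primary result and controlled alpha are untouched, as is the pooled descriptive ARR. No harm occurs if the SAP model is used. Version 11 also reports the double-blind period as complete, so the correction matters mainly for analyses and reporting that refer to the current protocol.

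Assumptions not in the documents: uniform accrual, balanced non-prognostic binary covariates, extension start uniform over 30–59 days after relapse, and a 4-year cap if 26 events are not reached. Monte Carlo error is about 0.4–0.9 points for the 3,000-trial runs and larger for the 400-trial check.

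**What to change.** Change the one sentence in Protocol 6.5.2 so that the response is the number of relapses, log(time at risk) is the offset, and treatment group, baseline ARR and region are the covariates, as in SAP 5.10.3.2. Reconcile Protocol 4.3.2.1 with SAP 5.2 by stating, in both documents, when a relapsing patient's time at risk ends for this analysis. The cost is one protocol sentence and one definition, with no new data and no change to the SAP model.
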